10.3.6 Measurement of Response for FDG-PET scans

Since it is extremely difficult to quantify the size of a lesion(s) by FDG-PET scan, the conventional RECIST criteria will not be used for the qualitative, non-SUV-based FDG-PET scan interpretation after chemoradiotherapy. Instead, the qualitative visual criteria from MacManus et al will be utilized, as follows:

Response Criteria: Evaluation of target lesions

*Complete Response (CR): CR will be defined as no tumor FDG uptake in the tumor bed, or activity in the tumor bed similar to that in the adjacent normal tissue;

Partial Response (PR): appreciable reduction in intensity of tumor FDG uptake or tumor volume apparent to the nuclear medicine physician when pre-, during-, and post-treatment PET scans are displayed side by side;

Progressive Disease (PD): appreciable increase in the intensity of tumor FDG uptake or volume of the tumor apparent to the nuclear medicine physician when pre-, during-, and post-treatment PET scans are displayed side by side.

Stable Disease (SD): no appreciable change in intensity of tumor FDG uptake or tumor volume between scans and no new sites of disease apparent to the nuclear medicine physician when pre-, during-, and post-treatment PET scans are displayed side by side;

** For these determinations, the pre-, during-, and post-treatment FDG-PET scans must be analyzed using the same display techniques to provide a consistent intensity of background soft-tissue activity.*

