2.0 OBJECTIVES

Primary objective: Delivery of SBRT to multiple sites in a safe and effective manner with acceptable toxicity

Primary Endpoints:

- Presence of multiple sites (between 2 and 5 sites)
- Acceptable toxicity: Grade 3 or less

Secondary Objectives/Endpoints:

- Quality of life (as measured by the FACT quality of life surveys, see appendix IV)
- Local control of metastatic sites (with measurable/quantitative assessment): proportion of patients with Complete Response (CR), Partial Response (PR), or Stable Disease (SD)
- Local control of primary site (with measurable/quantitative assessment): proportion of patients with local Complete Response (CR), Partial Response (PR), or Stable Disease (SD)
- Overall survival (OS)
- Two-year Overall Survival
- Analysis of patterns of failure post-SRS/SBRT (subsequent sites of failure and time to failure): proportion of patients with Progressive Disease (PD)

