10.4 Criteria for Discontinuation of Protocol Treatment

- Progression of disease as measured by RECIST criteria outlined above, PET scan RECIST criteria will be used for patients with follow-up PET scans, CT scan RECIST criteria will be used for patients with follow CT scan only.

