11.2 Sample size

Phase II studies are usually small trials, recruiting participants up to about 20, although often a lot less. However, we plan to analyze the data stratified by different primary cancer such as breast, prostate, and etc., since we are trying to detect which patient subsets are most likely to benefit from the proposed treatment. The sample size can be set at approximately 10 for each patient subset in order to have a reasonable estimate of overall survival, local control, and quality of life for each subset. We estimate that most of the patients will have breast, lung, and prostate primaries and that there will be smaller numbers with other primary types. Based on these assumptions, we estimate a sample size of 40 patients and expect a 10% drop-out rate and thus have set an estimated sample size of 44 patients.

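### The FDG-PET complete-response rule has no baseline-uptake condition and overlaps with progression without a precedence rule, so never-avid lesions can inflate the CR rate and bias local control upward

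*Combined protocol and SAP*

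**What the plan says.** Section 10.3.6 sets RECIST aside for PET and adopts published visual criteria. The rule for complete response reads: "CR will be defined as no tumor FDG uptake in the tumor bed, or activity in the tumor bed similar to that in the adjacent"; the comparison is with normal tissue beside the lesion. This describes only the scan being read.

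The other categories compare scans. PD is "appreciable increase in the intensity of tumor FDG uptake or volume of the tumor apparent to the nuclear medicine physician", and PR is "appreciable reduction in intensity of tumor FDG uptake or tumor volume apparent to the nuclear medicine physician". SD is the absence of appreciable change in either intensity or volume, with no new sites. PR, PD and SD are each read from pre-, during- and post-treatment scans shown together, and a footnote covering all the PET determinations says that "the pre-, during-, and post-treatment FDG-PET scans must be analyzed using the same display techniques". The section does not say which category applies when a lesion meets two.

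Section 2.0 lists "Local control of metastatic sites (with measurable/quantitative assessment") as a secondary endpoint, counted as the proportion of patients with CR, PR or SD. Local control of the primary site is defined in the same way. Section 11.2 wants local control estimated in subsets of about 10 patients.

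Section 10.4, which concerns stopping protocol treatment, states that "PET scan RECIST criteria will be used for patients with follow-up PET scans, CT scan RECIST criteria will be used for patients with follow CT"; the second half is for patients followed by CT alone.

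**The concern.** A response category should record a change brought about by treatment. PET CR, as written, can be met by a lesion that looked the same before treatment. The baseline FDG-PET/CT is mandatory, but it serves staging. Section 3.1.1 admits metastatic sites on radiographic and clinical grounds, and section 6.2.5 draws the target from CT, PET and clinical information together. A lesion at background on the baseline PET can therefore be enrolled, treated and assessed.

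Two things are at stake. First, the CR rate would include lesions that did not respond. Second, a background-level lesion that enlarges satisfies two definitions that fall on opposite sides of the local-control endpoint. Local control, and the proportion with PD in the patterns-of-failure analysis, would then depend on the reader's preference. In subsets of about 10, one such call is visible in the result.

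**Working it through.** **Plan's own figure.** Section 11.2 takes 40 patients and a 10% drop-out: 40 × 1.10 = 44, as stated. (Dividing instead, 40 / 0.90 = 44.4, rounds up to 45; nothing here turns on the difference.) The point does not depend on the sample size except as a denominator. One patient is 1/40 = 2.5 percentage points overall and 1/10 = 10 points in a subset of 10.

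**Applying the section 10.3.6 definitions to a lesion at background on the baseline PET** (taking the comparison as pre- versus post-treatment):

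| Course after SBRT | PET definitions met | Local control |
|---|---|---|
| Stays at background, size unchanged | CR and SD | Controlled either way |
| Stays at background, shrinks | CR and PR | Controlled either way |
| Stays at background, grows | CR and PD | Controlled or failed, depending on the reader |
| Takes up tracer above adjacent tissue | PD | Failed |

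The first two rows can distort the CR rate but not local control. Only the third row can bias local control.

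**Upper bound on that bias.** Let p be true local control and q the share of patients whose call rests on never-avid lesions read by PET. If every failure in that share stays at background and is called CR, and true control is the same in that share as elsewhere, then

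reported control = p + q(1 − p), so inflation = q(1 − p).

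The documents give no value for q; 5% to 30% is an assumption. For p, the Introduction (1.0) cites 77% of lesions controlled at 2 years in one series and 56% of treated sites in another trial. These are per-lesion rates, used here only as anchors for a per-patient endpoint.

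| q (assumed) | p = 77%: inflation (patients of 40) | p = 56%: inflation (patients of 40) |
|---|---|---|
| 5% | 0.05 × 0.23 = 1.2 points (0.5) | 0.05 × 0.44 = 2.2 points (0.9) |
| 10% | 2.3 points (0.9) | 4.4 points (1.8) |
| 20% | 4.6 points (1.8) | 8.8 points (3.5) |
| 30% | 6.9 points (2.8) | 13.2 points (5.3) |

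At most, reported control would be 78.2% to 83.9% instead of 77%, or 58.2% to 69.2% instead of 56%.

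**Scan schedule.** Appendix I marks FDG-PET/CT imaging before treatment and at follow-up and leaves the during-treatment cell blank. No other section schedules such a scan, and section 10.3.4 makes follow-up PET optional. The three-scan wording in 10.3.6 therefore does not match the schedule.

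**The case against.** The strongest reply is that the PD definition already deals with failing lesions. A non-avid lesion that becomes avid no longer meets CR and meets PD, and one that grows meets PD by volume. A reader might infer from the CR wording that a never-avid lesion is scored as controlled whatever it does. The documents do not support that, because both limbs of PD stand against it. What remains is the overlap. The volume limb does not remove it, since growth must be apparent on the PET display, the section itself concedes that size is very hard to quantify on PET, and nothing says that growth overrides CR.

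A reader might also infer that CR is the only PET category that the scheduled scans can satisfy. The footnote names the same three scans for every determination, CR included. A strict reading therefore blocks all four categories and a relaxed one blocks none. It is a mismatch with Appendix I and does not favor CR in particular.

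Nor does section 10.4 establish that PET outranks CT for local control. Its sentence governs discontinuation, and the plan states no modality rule for the endpoint, which is a gap of its own.

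It is also fair to say that the PET criteria come from a publication not available here, which may limit them to avid lesions; the protocol text does not. The plan states no hypothesis test for local control, so no error rate is affected.

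**Conclusion.** The concern holds in a limited form. PET CR lacks a baseline-uptake condition, so never-avid lesions meet it without any response. Because CR overlaps with PD and no precedence is stated, a non-avid lesion that grows can be called controlled or failed.

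The figures above are ceilings, not expected values. They assume a value for q, PET follow-up for every patient in that share, and a CR call for every failure there. Since follow-up PET is optional and some failures will show uptake or be called PD on volume, the actual effect should be smaller. A reader might go further and infer that the cancer subsets will differ because of tracer avidity. That would follow only if q differs by cancer type, and the documents give no avidity figures by type.

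The endpoints affected are secondary: local control and the proportion with PD. The primary toxicity endpoint and the sample size are not touched. The wording should be corrected, because the remedy is cheap and the subsets are small.

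**What to change.** In section 10.3.6, for the local-control endpoint:

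- Apply the PET categories only to lesions with uptake above adjacent normal tissue on the mandatory baseline FDG-PET/CT.
- Score all other lesions by CT size under section 10.3.5, using the CT part of the PET/CT where available. Section 10.3.5 classes bone and small lesions as non-measurable and gives response categories only for target lesions. Record such lesions as progressed or not progressed, and do not count them as CR.
- State that PD takes precedence when a lesion meets both CR and PD. This also settles avid lesions that lose uptake but enlarge.
- Replace the three-scan wording in the PR, PD and SD definitions and the footnote with pre- and post-treatment scans, to match Appendix I.

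Section 10.4 refers to RECIST criteria for PET, whereas 10.3.6 says RECIST is not used for PET. The two must be reconciled. No change to the discontinuation rule is proposed, and the edits above should be worded so that they do not alter it.

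The cost is protocol wording and one avidity field per lesion, read from a scan that every patient already has. The reported CR or local-control rate may come out slightly lower.

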10.4 Criteria for Discontinuation of Protocol Treatment

- Progression of disease as measured by RECIST criteria outlined above, PET scan RECIST criteria will be used for patients with follow-up PET scans, CT scan RECIST criteria will be used for patients with follow CT scan only.

11.0 STATISTICAL CONSIDERATIONS

Primary objective: Delivery of SBRT to multiple sites in a safe and effective manner with acceptable toxicity

Primary Endpoint(s):

- Presence of multiple sites (between 2 and 5 sites)
- Acceptable toxicity: Grade 3 or less

Secondary objectives/Endpoints:

- Quality of life (as measured by the FACT quality of life surveys, see appendix IV)
- Local control of metastatic sites
- Local control of primary site
- Overall survival (OS), Two-year Overall Survival
- Analysis of patterns of failure post-SRS/SBRT (subsequent sites of failure and time to failure)

11.1 Objectives of the proposed study

The primary objective of the proposed phase II study is to evaluate the feasibility of this curative intent treatment approach (SRS/SBRT to the metastatic disease sites in combination with standard curative therapy to the primary site) to patients presenting with oligometastatic disease.

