The outcomes of patients treated with SBRT for multiple organ metastases have also been reported. The University of Rochester reported an analysis on 121 patients with 1-5 metastases treated on two consecutive protocols. Patients on both protocols could have had previous therapy for their disease; only 27 patients had oligometastatic disease at initial presentation. The first protocol treated breast cancer patients with limited metastases, in which no brain lesions were treated. The second protocol included patients with cancer from any primary site and limited metastases including a brain primary. After treatment with ten fractions of 5 Gy over 2 weeks (10 fractions), metastatic lesions were controlled 77% of the time at 2 years (25). Milano (5) reported prospective data on breast cancer patients with oligometastatic disease (less than 5 sites) comparing patients treated with SBRT to those receiving only palliative therapy. Four-year survival was significantly improved in SBRT patients (59% versus 0%). University of Chicago (53) reported on a prospective trial in 29 oligometastatic patients (one to five sites and a life expectancy > 3 months, 81% had prior systemic treatment) who had 56 metastatic lesions treated with SBRT (3 fractions ranging from a total dose of 24 to 36 Gy). The authors found a control rate of 56% for treated sites and only 2 patients had grade 3 or higher toxicity.

From the data available, patients with oligometastatic disease appear to benefit in terms of disease control from SBRT. At this point, no one is able to adequately predict which patients have favorable oligometastatic disease and are good candidates for aggressive and potentially curative therapy and which patients are destined to have development of widespread metastatic disease. Some proposed factors for patients likely to proceed to widespread metastatic disease include size and grade of primary tumor, site of oligometastatic disease, and lymph node status. In order to best treat patients, it is important that careful studies be performed to collect clinical information on patients with oligometastatic disease to analyze patient subsets most likely to benefit from treatment.

While disease outcome is certainly an important endpoint, quality of life (QOL) also is of significant importance, especially in patients with metastatic disease that have traditionally thought to

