be incurable. It is important that, until aggressive treatment for oligometastatic disease becomes standard of care, careful attention is paid to the quality of life in treated patients. Multiple validated QOL surveys are available for a variety of cancer sites. Collection of such surveys will help to monitor the impact of treatment on QOL.

To our knowledge, there have not been any prospective trials examining the role of aggressive therapy in the treatment of oligometastatic disease only at initial presentation. None of the previously described reports include only patients at initial presentation; the majority of patients in the prospective and retrospective oligometastatic studies have had previous therapy. In order to better evaluate the role of curative therapy in patients presenting with oligometastatic disease we are proposing a prospective study of this patient cohort. Patients with oligometastatic disease (defined for this study as 5 or fewer sites of disease involving 3 or fewer organ systems) will receive SRS/SBRT to all sites of oligometastatic disease and standard curative therapy to the primary disease. The primary objective for this study will be feasibility with the potential for an eventual phase III study. In addition, clinical and translational information will be collected to better stratify patients with oligometastatic disease for future studies.

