6.2 Stereotactic Radiosurgery (SRS) and Stereotactic Body Radiation Therapy (SBRT)

See Appendix IV for site-specific SRS/SBRT details. The following are general guidelines.

6.2.1 SRS/SBRT Timing: All SRS/SBRT treatments will be completed within 3 weeks (preferably 2 weeks).

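### The primary objective is feasibility of delivering the treatment, but no endpoint or planned analysis measures delivery

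*Combined protocol and SAP*

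**What the plan says.** The primary objective appears in two scopes.

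- Section 11.1: "The primary objective of the proposed phase II study is to evaluate the feasibility of this curative intent treatment approach". The approach is spelled out there as SRS/SBRT to the metastatic sites combined with standard curative therapy to the primary. The Introduction agrees: "The primary objective for this study will be feasibility with the potential for an eventual phase III study".
- Section 11.0, with the same wording in the Summary and 2.0: "Primary objective: Delivery of SBRT to multiple sites in a safe and effective manner with acceptable toxicity". Treatment of the primary is not mentioned.

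Two primary endpoints are listed: "Presence of multiple sites (between 2 and 5 sites") and toxicity of Grade 3 or less. The secondary endpoints are quality of life, local control of metastatic and primary sites, overall and two-year survival, and patterns of failure.

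The protocol does set delivery standards, but as treatment instructions. Section 5.0 calls for every metastatic site to be treated, with SRS/SBRT and the start of primary treatment within 6 weeks. Section 6.2.1 says: "All SRS/SBRT treatments will be completed within 3 weeks (preferably 2 weeks").

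On numbers, 11.2 starts from 40 patients, and the authors "expect a 10% drop-out rate and thus have set an estimated sample size of 44 patients".

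**The concern.** A feasibility trial has to count how often the treatment was given as intended. Here the objective turns on delivery in both wordings, while the endpoints record something else. The stake is the next step: the Introduction presents the trial as a possible basis for phase III, and that decision would need to know what share of newly diagnosed patients can be taken through SRS/SBRT to all sites and on to curative primary treatment.

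Non-delivery is possible on the protocol's own account. External beam radiation, chemotherapy and surgery are generally started after SRS/SBRT is complete (6.1, 7.1, 8.1), so a patient can finish SRS/SBRT and not reach primary treatment. The Introduction says it cannot yet be predicted "which patients are destined to have development of widespread metastatic disease", and 10.4 gives as its criterion for stopping protocol treatment "Progression of disease as measured by RECIST criteria outlined above". Without a defined numerator, denominator and time window, any delivery figure would have to be constructed after the data were seen.

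**Working it through.** **Step 1. Match each planned measure to the objective.**

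- Having 2 to 5 sites: fixed at staging, before treatment. Section 3.1.3 sets an upper limit of 5 sites, and whether a patient has two or more is known at entry. It is not an outcome.
- Toxicity of Grade 3 or less: covers the acceptable-toxicity part of the objective in name, but not delivery. No rate, denominator, time window or threshold is given.
- Quality of life: does not record delivery.
- Local control, metastatic and primary: response of the lesions. It does not separate failure of the treatment from failure to give it.
- Overall survival, two-year survival and patterns of failure: same limitation.
- Section 11.3: Kaplan-Meier, log-rank and Cox analyses of survival, logistic regression for quality of life, and descriptive characteristics. There is no analysis of delivery.

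Nothing counts patients who had SRS/SBRT to every site, met the 3-week or 6-week window, or started or completed primary treatment.

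**Step 2. Reproduce the sample size.** Inputs from 11.2: base 40, drop-out 10%.

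- 40 × (1 + 0.10) = 44, the stated figure.
- The alternative, 40 / (1 − 0.10) = 44.4, rounds up to 45. The one-patient difference does not matter here.
- The base of 40 rests on about 10 patients per primary-cancer subset for survival, local control and quality of life. Feasibility does not enter it.
- Allowed drop-outs: 44 − 40 = 4. Section 11.2 does not define drop-out or say how drop-outs are analysed.

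**Step 3. What a delivery endpoint would look like at N = 44.** The exact (Clopper-Pearson) 95% limits for x delivered out of n are: lower = 2.5% quantile of Beta(x, n − x + 1); upper = 97.5% quantile of Beta(x + 1, n − x).

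- Assumption: the four allowed drop-outs are all delivery failures and no one else fails. Then x = 40, n = 44, and 40/44 = 90.9%. Limits: Beta(40, 5) gives 78.3% and Beta(41, 4) gives 97.5%.
- For precision only, at two other arbitrary values: 33/44 = 75.0% (59.7% to 86.8%) and 22/44 = 50.0% (34.6% to 65.4%). The documents give no reason to expect either.
- Why the denominator must be stated: if the same four patients were left out, the figure would be 40/40 = 100% (91.2% to 100%). No document says this would be done; none says it would not.

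**The case against.** The best defence is that the site-count endpoint is a badly worded delivery endpoint, meaning SBRT delivered to 2 to 5 sites, and that eligibility already screens for deliverability: metastases must be treatable with SRS (3.1.4), the primary must be treatable with curative intent (3.1.5), and patients unable to obtain SRS/SBRT through insurance or payment are excluded (3.2.10). The screens should reduce non-delivery, and that part stands. But they do not measure it, and even the generous reading of the endpoint leaves out completeness, timing and all primary treatment.

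A reader might infer several stronger things that the documents do not support.

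- That 11.2 removes drop-outs from the analysis. It does not say so. The 10% may simply cover loss to follow-up for the secondary outcomes, and 11.3 calculates survival for all patients from enrollment. The fair statement is that 11.2 is silent.
- That the trial could meet its toxicity endpoint, or declare feasibility, despite poor delivery. No rule exists by which either could be met or declared. What is missing is a measure.
- That poorer delivery would make the approach look safer. SRS/SBRT ideally comes first (5.0), so a patient who never starts primary treatment will often have had full SRS/SBRT exposure. The argument reaches only interrupted SRS/SBRT or the toxicity of the combination.
- That progression before primary treatment is the main threat. Appendix I schedules imaging and response evaluation only before treatment and at follow-up, so 10.4 has little scheduled opportunity to act in that interval. The documents give no rate from which to build such a scenario.

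**Conclusion.** The point holds as a mismatch between objective and endpoints. Feasibility of delivery is the primary question in both wordings, and no primary endpoint, secondary endpoint or planned analysis measures it. This rests on the text alone and needs no assumed rate. It is more than missing detail, because the endpoints that are listed do not measure the stated objective.

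Its numerical size is not known. The figure of 90.9% (78.3% to 97.5%) is an illustration that assumes the allowed drop-outs are the only delivery failures; it is not a forecast. The arithmetic behind 44 is not in question, and the point makes no claim about how drop-outs will in fact be handled.

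**What to change.** 1. Reconcile the primary objective across the Summary, Introduction, 2.0, 11.0 and 11.1: either delivery of SRS/SBRT, or delivery of SRS/SBRT plus curative primary treatment.
2. In 2.0 and 11.0 (and the Summary), replace the site-count endpoint with a delivery endpoint: the proportion of all enrolled patients who receive SRS/SBRT to every identified metastatic site within the protocol's 3-week window (6.2.1). If the 11.1 scope is kept, also require the start of curative primary treatment within the 6-week window of 5.0. First state from which SRS/SBRT date that window is counted, and how it applies when surgery on the primary comes first, as 5.0 allows.
3. Count patients who drop out, progress, refuse or die before these steps as not delivered.
4. In 11.3, report the proportion with an exact 95% CI, the reasons for non-delivery, and the proportion completing primary treatment.
5. In 11.2, state that drop-outs stay in this denominator.

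This yields an estimate, not a pass or fail. If the sponsor wants a decision rule, it must also name a minimum acceptable rate, which the documents do not supply.

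Cost: wording changes, with no added patients or visits. Start and completion dates of primary treatment must be abstracted from treatment records, since 4.2 lists a single treatment start date and Appendix I has no entry for primary treatment. The reported feasibility figure will be less favourable than one confined to patients who stay on treatment.
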